One limitation of current AID systems is that they have no knowledge about the context or environment that a person is currently experiencing. Contextual patterns can potentially improve the performance of an AID by recognizing environments or patterns of living that are related to changes in glucose. The team at OHSU is developing a context-aware glucose prediction algorithm that will capture context data from the patient both indoors and outdoors. This context data will be provided to the algorithm to allow for detecting contextual patterns that might relate to hypo- or hyperglycemia. The goal of this study will be the creation of a data set that will include contextual patterns along with glucose, insulin and physiological data. Participants will complete meals and exercise at specific times. The purpose of the prescribed meals and exercise sessions is to generate ground truth patterns that will be used in the design of the context-aware glucose prediction algorithm.

Primary Objective

- To assess the accuracy of the context-aware glucose prediction by comparing glucose prediction values against the Dexcom G6 CGM values using mean absolute relative error (MARE)
- To assess the accuracy of the context-aware glucose prediction by comparing glucose prediction values against the Dexcom G6 CGM values using mean relative error (MRE).

Study Hypothesis:

- The study hypothesis is that context pattern data will improve the accuracy of the prediction of hypoglycemia and hyperglycemia in the context-aware glucose prediction algorithm.

Primary Endpoints:

- Comparison of the accuracy of hypoglycemia prediction comparing glucose prediction values against the Dexcom G6 CGM values using mean absolute relative error (MARE).
- Comparison of the accuracy of hypoglycemia prediction comparing glucose prediction values against the Dexcom G6 CGM values using mean relative error (MRE).

Study Type

This is a single center randomized prospective study measuring the accuracy of the context-aware glucose prediction against the Dexcom G6 CGM values.

Study Population

[figure not shown]
Study population will be adults with type 1 diabetes, ages 18 – 65 years of age. Older subjects are excluded due to higher risk of unrecognized coronary artery disease. Younger subjects are excluded as it is appropriate to assess safety and efficacy first in the adult population. Thirty subjects will be recruited to participate in studies.

Protocol Summary:

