Up to 75 subjects may be screened in this study. Goal enrollment is 30 subjects.

Withdrawal Criteria

The subject may withdraw at will at any time or at the discretion of the Investigator.

A subject must be withdrawn if the following applies:

1. Hypoglycemia during the treatment period posing a safety problem as judged by the investigator.
2. Hyperglycemia during the treatment period posing a safety problem as judged by the investigator.
3. Protocol deviation having influence on efficacy or safety data as judged by the Investigator.
4. Substantial and repeated non-compliance with trial procedures.
5. Pregnancy.
6. Intention of becoming pregnant.

Visit Procedures

Staff will confirm participant and household do not have COVID-19 or symptoms of COVID-19 prior to conducting any face-to-face visits. In order to minimize face to face contact with participants per OHSU Covid-19 policy, there is the option to complete some visits virtually.

Screening (Visit 1)

Screening will take place within 12 weeks prior to Visit 2. All screening visits will take place at OHSU's Oregon Clinical Translational Research Institute (OCTRI) outpatient clinic, the

Biomedical Engineering Point of Care (BME POC) Laboratory or at the Harold Schnitzer Diabetes Health Center. The subject will be sent the consent form prior to the screening by email so that they can have time to read it fully at their leisure and prepare any questions they might have. Upon arrival at the clinic and prior to any procedures, study staff will explain the study, give the subject ample time to ask questions and consider participation, and ensure that subject voices understanding of the informed consent and study requirements. To minimize the possibility of coercion and to ensure that subject is signing the appropriate version of consent, an informed consent checklist will be used by study staff. After the subject has signed the consent, a copy of the consent/authorization form will be given to the subject. The original will be kept for the source document.

A capillary blood glucose (CBG) will be obtained and measured by a Contour Next glucose meter and recorded after consenting. Prior to measurement of any blood samples, the meter will undergo quality control testing with two different glucose levels, one high and one low, and both values must fall within the accepted range for a meter to be used.

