Statistical methods

The hypothesis of this study is that we will be able to identify contextual patterns in the movement data that will relate to glycemic outcomes. We will use machine learning techniques

including k-means clustering and Gaussian mixture models to group contextual patterns and then relate these groups of patterns with glycemic outcomes including the following:

- Time in hypoglycemia (<70 mg/dL)
- Time in hyperglycemia (>180 mg/dL)
- Time in a target range (70-180 mg/dL)
- Mean glucose
- Glucose variability (standard deviation and coefficient of variance).

We will evaluate if the clusters of contextual patterns are related to differences in glycemic outcome measures using generalized estimating equations, which takes into account correlated data and repeated measures. Data will be analyzed using an intention-to-treat analysis and missing sensed glucose values will be interpolated for up to 20 min segments.

Confidentiality and Protection of Human Subjects

RISKS and BENEFITS

Risks: The risks of the protocol procedures are considered minor. Subjects will be managing their own blood glucose as they normally would.

Risks from exercise include falls, sprains, bruises, very low risk of bone fractures and head trauma. The likelihood of significant harm is quite low.

There is a small risk of sensor fracture, and in such a case, a piece of the sensor could be left in the tissue after sensor removal. For this reason, the study investigator will inspect each removed sensor for the possibility of breakage or fracture. Any evidence of sensor breakage will be recorded and reported to the sensor company.

Benefits: The subject may not directly benefit from being in this study; however, their participation may help to advance automated insulin decision support software.

COSTS:

Subjects will receive \$500 for completion of all study visits. If subjects withdraw early from the study, compensation will be given as follows: \$125 per 7 study days in the study. If the subject completes a partial week, the subject will also receive \$125 for the partial week. There is no compensation for the screening visit. Additional reimbursement will be available for participants who complete protocol requirements to help compensate for their time. The payment amount will be specified in the informed consent form.

Monitoring Entity:

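### The GEE analysis of context clusters states no small-sample correction for about 30 participants; in its usual form, a joint cluster test would reject too often, and increasingly so with more clusters.

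*Combined protocol and SAP*

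**What the plan says.** Statistical methods gives as the study hypothesis that "we will be able to identify contextual patterns in the movement data that will relate to glycemic outcomes". Machine-learning methods, "including k-means clustering and Gaussian mixture models to group contextual patterns", form the groups. Then: "We will evaluate if the clusters of contextual patterns are related to differences in glycemic outcome measures using generalized estimating equations", a method "which takes into account correlated data and repeated measures". The outcomes listed are time below, above and in range, mean glucose, and glucose variability as SD and coefficient of variation.

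On sample size, Study Population says "Thirty subjects will be recruited to participate in studies" and Subject Recruiting says "Goal enrollment is 30 subjects". Withdrawal Criteria allows the number to fall: "The subject may withdraw at will at any time or at the discretion of the Investigator".

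No section gives a working correlation, variance estimator, reference distribution, small-sample correction, test level, number of clusters or record unit for the GEE.

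The primary endpoints are separate. They concern prediction error, for example "Comparison of the accuracy of hypoglycemia prediction comparing glucose prediction values against the Dexcom G6 CGM values using mean absolute relative error (MARE", and the matching endpoint for mean relative error.

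**The concern.** GEE does allow for repeated measures, but its usual sandwich variance is justified by a large number of independent units. Here those units are the participants, about 30 or fewer. Twenty-eight days of records per person do not add units. With few units the sandwich variance is too small on average and is itself noisy, and a chi-square reference ignores that noise. The effect grows with the number of coefficients tested together, and a cluster factor with K levels has K−1 of them.

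At stake is the only inferential method named in Statistical methods, applied to the hypothesis stated there. A finding that context clusters relate to glucose could be a false positive more often than its nominal level implies.

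**Working it through.** **Inputs from the plan.** N = 30 participants; 28 days on study.

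**Assumptions, because the plan gives none.** 5% test level; one record per participant-day (28 records); K = 2 to 5 clusters; between-person and within-person SD of 25 and 35 mg/dL; no true effect; one outcome at a time; cluster labels treated as fixed. The plan has no figure of its own to reproduce here.

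**Step 1: exact benchmark.** Suppose every participant uses the clusters in perfect balance, and let p = K−1. The uncorrected Wald statistic is then W = T²·N/(N−1), where T² is Hotelling's statistic and T²(N−p)/[(N−1)p] follows F(p, N−p). The usual test rejects when W exceeds the chi-square 95% point, so its true size is

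P[ F(p, N−p) > χ²(p, 0.95)·(N−p)/(N·p) ].

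| K | Threshold used, N = 30 | Correct F 95% point | True size, N = 30 | True size, N = 24 |
|---|---|---|---|---|
| 2 | 3.841×29/30 = 3.713 | 4.183 | 6.4% | 6.8% |
| 3 | 5.991×28/60 = 2.796 | 3.340 | 7.8% | 8.6% |
| 4 | 7.815×27/90 = 2.344 | 2.960 | 9.5% | 10.9% |
| 5 | 9.488×26/120 = 2.056 | 2.743 | 11.6% | 13.7% |

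N = 24 is an assumed illustration of withdrawals. This benchmark needs no assumption about the SDs or the within-person correlation.

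**Step 2: uneven cluster use, by simulation.** Cluster use ranged from even to concentrated but varied within most participants. Working correlation was independence or exchangeable. Further settings had a skewed outcome, 14 or 56 records per person, and SDs of 12/40 and 35/35.

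| K | Uncorrected joint test, N = 30 | N = 24 |
|---|---|---|
| 2 | 6–8% | 7–10% |
| 3 | 7–10% | 8–12% |
| 4 | 9–14% | 11–15% |
| 5 | 11–17% | 14–21% |

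Single coefficients at N = 30, uncorrected, rejected 5–10% of the time. The statsmodels GEE routine with its default robust covariance gave 6.4–7.4% at K = 2 and 12–14% at K = 5.

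**Step 3: rare or person-specific clusters.** Uncorrected rejection was 12–14% at K = 2 with one cluster holding about 2% of records, and 19–24% at K = 5 with rare clusters or clusters constant within a person. It was 22–34% when a rare cluster was concentrated in a few people.

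**Step 4: the corrected test.** Take W from the Mancl-DeRouen covariance and refer W(N−K+1)/[(N−1)(K−1)] to F(K−1, N−K+1).

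- *Balanced use.* The covariance is multiplied by (N/(N−1))², so rejection requires F > F(0.95)·30/29. At K = 5 this is 2.743×30/29 = 2.838, for a size of 4.5%. At K = 2 the size is 4.7%.
- *Clusters varying within most participants.* Size is about 4–6% with exchangeable correlation. Across all settings, including independence, it is about 2–6%, so independence leans conservative.
- *Corrected covariance with chi-square kept.* Size remains 6–9% at K = 4 and 8–11% at K = 5, so the F reference is needed too.
- *Rare, person-concentrated clusters.* Size is still 5–12.5%, and 10–17% with a cluster confined to three participants. The correction helps but does not restore 5%.

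**Step 5: working correlation.** Let cluster membership depend on the previous record's glucose but have no concurrent association. At K = 2 the corrected test then rejected 7–11% of the time with exchangeable correlation, against 4–5% with independence. At K = 5 it was 5–8% against 4–5%.

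**Step 6: power, balanced use, N = 30.** Take the effect at which an exact 5% test has 80% power. The corrected test has 79.0%, 78.5% and 78.4% at K = 2, 4 and 5. The uncorrected test shows 83.1%, 88.0% and 90.2%, but only because its size is inflated.

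**The case against.** The strongest reply is that the plan is silent here and not wrong. The excess needs four choices that Statistical methods does not make: an uncorrected sandwich variance, a chi-square reference, a joint test, and several clusters. With 2 clusters or single contrasts the effect is small, and a statistician might correct without being told. This stands, and it is why the point is conditional. But nothing in the plan limits the number of clusters or excludes the usual form.

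A second reply is low consequence. The study exists to build a data set for algorithm design, and the cluster analysis drives no treatment decision. Several outcomes and two clustering methods carry no multiplicity rule, which is a separate gap. This also stands: it limits the weight of the point without removing it.

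A reader might infer that the study's main result is at risk. The documents do not support that: the primary endpoints are MARE and MRE of predicted against CGM glucose, and the GEE is not tied to them. A reader might also take the percentages as bounds, or the correction as restoring 5% everywhere. Steps 3 and 4 show that neither is so.

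**Conclusion.** The concern holds in a limited, conditional form. With about 30 participants, usual-form GEE with a joint cluster test at an assumed 5% level rejects under no effect about 6–8% (2 clusters), 9–14% (4) or 11–17% (5) of the time, when clusters vary within most participants. The balanced-use figures of 6.4%, 9.5% and 11.6% are exact under normality. The wider ranges rest on the assumed record unit, SDs and cluster-use patterns, and rare or person-specific clusters exceed them.

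This is a worthwhile, inexpensive improvement to a non-primary analysis. It does not show that the plan has specified an invalid test.

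**What to change.** Add to Statistical methods, before context clusters are linked to glucose outcomes:

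- **Variance and references.** GEE will use a Mancl-DeRouen bias-corrected covariance. Single coefficients will be tested by t on N−K df. The overall cluster test will refer W(N−K+1)/[(N−1)(K−1)] to F(K−1, N−K+1), where W is the Wald statistic from the corrected covariance, N the participants analysed and K the clusters. These df assume that the cluster factor is the only term besides the intercept.
- **Working correlation.** Use independence, or report it alongside exchangeable, because context may follow earlier glucose.
- **Sparse clusters.** Merge, or report descriptively only, any cluster contributed by fewer than a stated minimum number of participants. Set that minimum before outcomes are linked.
- **Number of clusters.** Fix K from context data only, before outcomes are linked: for example BIC for Gaussian mixtures, and a silhouette or gap criterion for k-means.
- **Level and unit.** State the test level and the record unit, for example participant-day.

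The cost is wording only, with no new data or participants. The covariance is a standard software option (bias_reduced in statsmodels) and the scaled F is one line of arithmetic. Single-coefficient intervals become about 8–22% wider with 30 participants (11–29% with 24). Under balanced use, power falls about 1–2 points below an exact 5% test. The power cost under concentrated cluster use has not been quantified.

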Subjects will be on study for 28 days. Sensor glucose, activity, exercise, insulin, indoor and outdoor contextual patterns and meal data will be collected during this time. Subjects will wear the Dexcom G6 CGM system and a FitBit Ionic (or similar FitBit), Polar, Garmin or Apple Watch physical activity monitor for the entire 28 days. Physical activity monitors will send data to the iPancreas mobile app created by OHSU. iPancreas will be supplied to participants on a separate study-provided phone. Subjects will continue to use their own insulin pump. Subjects will be asked to also wear a MotioWear indoor/outdoor context-aware tracking tag and to install the MotioWear beacons within their home. Subjects will be randomized to complete either aerobic, high intensity interval training, or resistance exercise videos twice weekly at home during weeks 1 and 2 and once weekly during weeks 3 and 4. Subjects will also ingest a self-selected meal prior to these prescribed exercise sessions. Subjects will consume a high carbohydrate dinner once each week on the same day, at approximately the same time (but not on the exercise days).

Subjects will use the T1 DEXI mobile app created by OHSU to capture meal and exercise data along with photos of meals over the 28 day period. Subjects will take photos of their food the day of and the day after they complete the exercise video. While at home, subjects will check CBG before and after exercise, for symptoms of hypoglycemia, and for Dexcom G6 alarms for sensor <70 mg/dL and >250 mg/dL. See **Figure 1** below for a diagram of the study flow. The study investigators retain the authority to modify any aspects of the protocol at his/her discretion if he/she believes the subject's safety is a concern.

Figure 1: Study Flow Design

Background on MotioWear System

Our group at OHSU has developed a unique context measurement system in collaboration with MotioSens (Portland OR) called MotioWear. MotioWear (Figure 2) is comprised of a wearable tag, beacons that are plugged in around a home, and a data hub that captures the movement

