Subjects will be randomized to complete either aerobic, high intensity interval training, or resistance exercise videos twice weekly at home during weeks 1 and 2 and once weekly during weeks 3 and 4. Subjects will be instructed to complete the exercise for the video sessions in the same location in their home on the same day at approximately the same time. The exercise videos are approximately 30 minutes long. A list of exercises to be performed is provided in Appendix E. Subjects will also ingest a self-selected meal prior to these prescribed exercise sessions. Instructions for the exercise will be provided via video links. Subjects will be instructed to check a CBG before initiating exercise to ensure safety. Subjects will be instructed to consume a snack if glucose is <120 mg/dL and delay exercise until glucose is >80 mg/dL. Also, if glucose is >250 mg/dL, subjects will be instructed to calculate if a correction dose is needed and delay exercise until glucose is <250 mg/dL. Subjects will enter information about exercise into the T1 DEXI app. Subjects will receive reminders via phone or text to complete their exercise and to monitor adherence to protocol. Participants may also receive reminders to enter activity information through the T1DEXI app. Subjects will also be instructed to check a CBG after exercise and consume a snack if needed.

Subjects will consume a high carbohydrate dinner prepared by OHSU Bionutrition once each week on the same day at approximately the same time (but not on the exercise study video days). The meals can potentially be picked up all at once and frozen until use.

Subjects will be able to contact study staff for any issues with the devices. Study staff will follow-up with subjects every 7 days. Subjects may receive text messages from study staff with study reminders/instructions or clarification of meal photos. This visit should take approximately 1.5 hours, depending on subject experience. Participants will be asked to download his/her pump weekly or biweekly during the 28 days on study. This will allow for frequent data capture in case of a battery change or loss of power to the pump which can erase insulin data.

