- A custom app developed by OHSU called T1-Dexi will also be installed on the subject's phone or on a provided study phone. The T1-Dexi app has undergone a security review by OHSU IT and the results of this can be provided upon request.
- A custom app developed by OHSU called iPancreas will be installed on a provided study phone. The iPancreas app has undergone a security review by OHSU IT and the results of this can be provided upon request.

The T1-Dexi app will serve as the 'data aggregator' on the phone and will perform the following functions:

- T1-Dexi app will collect self-report meals and exercise data from the participants both as text / categorical selections and also as food photographs collected from the camera on the phone.
- Data is collected by the T1-Dexi app and this non-medical, deidentified data is pushed to the OHSU-version of the Amazon Web Services (AWS) Cloud instance. The following data is pushed to the Dexi AWS server:

- a. Photographs of the user's food as taken on their smart phone camera
- b. Food types and amounts as acquired by the T1-Dexi app
- c. Exercise types and amounts as acquired by the T1-Dexi app
- d. Insulin pen data acquired through Apple Health Kit
- Physical Activity Data is collected by the iPancreas app and this non-medical, deidentified data is pushed to the OHSU-version of the Amazon Web Services (AWS) Cloud instance. The following data is pushed to the iPancreas AWS server:
 - a. Heart rate
 - b. Accelerometry
 - c. METs
- The data stored within AWS is de-identified and does not contain any information from the 18 HIPAA designations of personally identifiable information.

Day 28 Study Completion visit:

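### Exercise type is randomised but is not named in any endpoint or model, so the cluster analysis should adjust for it and the plan should say what randomisation and intention-to-treat mean here

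*Combined protocol and SAP*

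**What the plan says.** The Study Type section labels the design as randomised: "This is a single center randomized prospective study measuring the accuracy of the context-aware glucose prediction". The factor randomised is given in the Protocol Summary ("Subjects will be randomized to complete either aerobic, high intensity interval training, or resistance exercise videos twice weekly") and again under the Study Start-up Visit. In the text available, it is the only randomised factor.

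The opening section gives the prescribed meals and exercise a data-generating purpose: they provide reference patterns for designing the prediction algorithm. The primary endpoints are MARE and MRE of hypoglycaemia prediction against the CGM. Neither mentions exercise arm.

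Statistical methods groups contextual patterns by k-means and Gaussian mixture models. It then relates the groups to time below, above and in range, mean glucose and glucose variability, "using generalized estimating equations, which takes into account correlated data and repeated measures". Arm is not named as a factor, covariate, stratum or summary, and no working correlation is given. The same section promises that "Data will be analyzed using an intention-to-treat analysis", without defining the analysis set or naming a contrast. The Data Collection section does record "Exercise types and amounts as acquired by the T1-Dexi app", but assigns this to no analysis.

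The Withdrawal Criteria open with "A subject must be withdrawn if the following applies". The list includes "Protocol deviation having influence on efficacy or safety data as judged by the Investigator" and substantial, repeated non-compliance with trial procedures.

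**The concern.** A trial that randomises and promises intention-to-treat would normally analyse something by randomised group. Here nothing is, so the sentence gives the analyst no instruction.

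The practical risk lies in the one inferential model that the plan specifies. The three videos consist of different movements, so a movement cluster could occur mainly in one arm. If that arm also has a different glucose level, the coefficient for the cluster partly measures arm, and a contextual pattern would be credited with a difference that belongs to the exercise programme.

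There is a second, smaller issue. Intention-to-treat is meant to keep people in the analysis whatever their adherence, whereas the withdrawal rules end participation on adherence grounds. The plan does not say explicitly how the data of a withdrawn participant are used.

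**Working it through.** The plan gives no figure to reproduce on this point: no allocation ratio, effect size, SD or withdrawal rate. What follows is an illustration of size, not evidence of bias.

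**Inputs from the documents.** 30 participants, 28 days, three exercise types, and 2 + 2 + 1 + 1 = 6 prescribed sessions each.

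**Assumptions.** Equal allocation (30/3 = 10 per arm); one analysis window per day, so 280 windows per arm and 840 in all; true cluster effect zero in case A; one arm's mean glucose 10 mg/dL higher, either on all days (case A) or only on its session days (case B). A cluster occurs on 6 of 28 days in that arm and on either 3 of 28 days or none in the other two arms. That places 50% or 100% of the cluster's windows in the one arm.

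**Case A: difference on all 28 days, working independence.** The unadjusted coefficient shifts by the arm difference times (share of cluster windows from the arm minus share of other windows from it).
- Half of the cluster's windows from the arm: 60/120 − 220/720 = 0.500 − 0.306 = 0.194.
- All from the arm: 60/60 − 220/780 = 1.000 − 0.282 = 0.718.

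For an arm difference of 5 to 10 mg/dL this is 0.194 × 5 = 1.0 to 0.718 × 10 = 7.2 mg/dL.

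**Case A, exchangeable structure.** This was simulated with a within-person SD of 30 mg/dL and a between-person SD of 10 or 30 mg/dL (assumed), and a 10 mg/dL arm difference. The mean shift was 0.08 to 0.46 mg/dL (half of the windows) and 0.31 to 1.80 mg/dL (all). That is 0.01 to 0.18 of the arm difference, or 0.04 to 1.8 mg/dL for a difference of 5 to 10 mg/dL. With arm in the model, the cluster coefficient returned to zero within simulation error under both structures.

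**Case B: the same 10 mg/dL only on that arm's session days, taken as its cluster days; working independence.**
- Half of the windows: the unadjusted coefficient is 10 × 60/120 = 5.00. Adjusted for arm, it is a weighted mean of the within-arm contrasts (10 in the one arm, 0 in the others). The weights are 280 × (6/28) × (22/28) = 47.1 and 560 × (3/28) × (25/28) = 53.6. This gives 10 × 47.1/100.7 = 4.68, a change of 0.32 mg/dL.
- All of the windows: 10 either way, a change of 0.

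Under an exchangeable structure the simulated change was about 0.1 mg/dL or less.

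**Precision.** Across the simulated settings, the standard error of the cluster coefficient with arm was 0.45 to 1.02 times that without it.

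**By-arm comparison.** With 10 v 10, two-sided 5% and 80% power, the detectable difference is about 1.32 SD.

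**Withdrawal.** Planned collection is 30 × 28 = 840 participant-days. One withdrawal at the end of day 7 loses 21 days (21/28 = 75% of that person's record; 21/840 = 2.5% of the total). One at the end of day 21 loses 7 days (25%; 0.8%).

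**The case against.** The strongest reply is that no treatment comparison was ever intended. The protocol says what the sessions are for, and randomisation plausibly just spreads exercise types across the data set. This stands. It removes any reading in which the absence of an arm contrast is itself a failure, and prediction error against the CGM involves no between-arm estimate. It does not explain what intention-to-treat is doing in the plan.

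Next, exercise may reach the analysis indirectly, through recorded exercise types or through the clusters themselves. That is possible, but the plan does not say so. The point is therefore limited to arm as a named term.

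Third, the larger shifts require a difference that lasts all 28 days, while the prescribed exercise is six sessions of about 30 minutes: 3 of 672 hours, or 0.45%. If the effect is confined to session days, the cluster coefficient is the context–glucose association that the plan seeks, and adjustment barely moves it. This also stands. Carry-over could put the truth between the two cases. A shared schedule and a fixed exercise location at home also make a single-arm location cluster less likely.

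Finally, a marginal association is a legitimate target and exercise is part of context. That is why results should be shown both ways and not only adjusted.

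On withdrawal, a reader might infer that non-compliant participants are dropped from the analysis. The documents do not support that. The criteria end participation and delete nothing, and the Recording of Data section says that collected data will be used for the endpoints.

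**Conclusion.** The point holds as a low-cost improvement to the plan. Exercise type is randomised and intention-to-treat is promised, but no endpoint or model uses arm by name.

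A reader might infer that the cluster results will be biased by several mg/dL. The documents do not support that. The shift of 0.19 to 0.72 of the arm difference rests on working independence, a cluster concentrated in one arm and a glucose difference on every day. It falls to 0.01 to 0.18 under an exchangeable structure, and to 0.32 mg/dL or less (independence) for a 10 mg/dL effect confined to session days. Which case applies, and which working correlation will be used, cannot be told from the documents. The primary endpoints are not affected.

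The withdrawal rule is in tension with intention-to-treat, not in contradiction with it. No bias from it is shown, and the documents give no withdrawal rate.

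**What to change.** In Statistical methods:
- Include randomised exercise type (three levels) as a covariate in the GEE models, name the working correlation, and report cluster associations with and without the covariate.
- Report MARE and MRE by arm descriptively only.
- State the role of randomisation, for example to give a balanced variety of exercise data, if that is the intent.

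As a secondary clarification, reconcile the Withdrawal Criteria with the intention-to-treat statement. State that all randomised participants are analysed on all recorded data, including data before withdrawal, and report withdrawals by arm and reason. This does not recover days left uncollected after withdrawal. It changes no withdrawal rule made for safety or pregnancy.

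The cost is a few sentences and a field for withdrawal reason on an existing form. No visits, devices or measurements are added, because arm is known from randomisation. The statistical price is two model degrees of freedom with 30 participants. In simulation the standard error rose by at most about 2%, and fell under working independence.
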